#### 7.8 Regression analyses

For the application of regression analysis, missing/unknown data for prognostic factors are imputed. Imputation is planned to be accomplished by a regression based single imputation method where missing values of one predictor variable are predicted by regression models with a set of remaining potential prognostic variables as independent variables. This might require adequate preprocessing of the data. Modification of this imputation strategy is possible if implied by the data.

Regression analyses will be evaluated for FAS and conducted on imputed data.

Regression analyses will be performed separately for each of the two primary variables (see Section 6.4):

LCIG monotherapy 1 (LCIG monotherapy 2, respectively) at 12 months after LCIG initiation will be used as dependent (i.e. response) variable in two multivariable logistic regression models. The independent variables (i.e. potential predictors) will be checked for collinearity.

For the first multivariable logistic regression model the following variables will be considered as potential predictors (i.e. independent variables):

Table 7-2: Potential predictors used for regression analysis 1

Variable	Range	Dichotomization/Grouping
Age	numeric	-
Gender	Male, Female	Male vs. Female
Race	White, Black, Asian, Mixed, Other	White vs. Non-White
Education	No formal education, primary school, secondary school, non-university professional education, university	Less than secondary school vs. secondary school or higher
Total number of symptoms	numeric	
Number of symptoms related to treatment	numeric	
Number of motor symptoms	numeric	-
Number of non-motor symptoms	numeric	-
Total daily LEDD at LCIG initiation	numeric	-
Time from PD diagnosis to start of LCIG	numeric	-
Duration of 'Off' state time during a 24h period	numeric	-
Duration of dyskinesia during a 24h period	numeric	-
UPDRS V prior to LCIG initiation (if available)	numeric	-
Any device aided therapy other than LCIG in the past	Yes, No	Yes vs. No
Any dopamine agonists in the past	Yes, No	Yes vs. No
PD motor phenotype	Tremoric, Akinetic rigid, Mix	
Time from PD diagnosis to motor fluctuation	numeric	
Time from PD diagnosis to onset of morning akinesia	numeric	
Country		
GNI	numeric	

Categorical predictors will be dichotomized / grouped as shown in Table 7-2 in order to simplify interpretation.

Backward elimination with a significance level of 0.05 will be applied to stepwise automatically select relevant predictors. Effect estimates and p-values will be given for each (potential) predictor.

For the second multivariable logistic regression model the following variables will be considered as potential predictors (i.e. independent variables):

Table 7-3: Potential predictors used for regression analysis 2

Variable	Range	Dichotomization/Grouping
Approximate number of APD patients treated per year	numeric	-
Years of LCIG experience	numeric	-
Years of DBS experience	numeric	-
Approximate number of APD patients treated with LCIG per year	numeric	-
Number of years physician has been working at the institution	numeric	-
Average number of PD and APD patients per year at center	numeric	-
Number of specialist physicians working with PD patients at center	Numeric	-
Origin of service at center	National health services, Private health services	National health services vs. Private health services
Average frequency of routine visits for APD patients on device aided therapy at center	< 1x/year, 1x/year, 2x/year, 3x/year, > 3x/year	≤ 1x/year vs. ≥ 2x/year
Country		
GNI	numeric	

Categorical predictors will be dichotomized / grouped as shown in Table 7-3 in order to simplify interpretation.

Backward elimination with a significance level of 0.05 will be applied to stepwise automatically select relevant predictors. Effect estimates and p-values will be given for each (potential) predictor.

For both regression models the Gross National Income (GNI) is defined as follows (source: https://data.worldbank.org/indicator/NY.GNP.PCAP.CD):

Country	GNI
Austria	45.44
Bulgaria	7.76
Canada	42.87
Czech Republic	18.16
Croatia	12.43
Estonia	18.19

Greece	18.09
Hungary	12.87
Ireland	55.29
Israel	37.27
Netherlands	46.18
Romania	9.97
Spain	27.18
Sweden	52.59

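### Missing predictors are filled once by regression, without the outcome, and then analysed as observed; the harm depends on an unstated choice and on unknown missing rates

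*SAP*

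**What the plan says.** SAP 7.8 plans two multivariable logistic models for each monotherapy definition. The response is fixed: "LCIG monotherapy 1 (LCIG monotherapy 2, respectively) at 12 months after LCIG initiation will be used as dependent (i.e. response) variable".

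Missing or unknown predictor values are filled first, by a "regression based single imputation method where missing values of one predictor variable are predicted by regression models". The inputs to those models are the other candidate predictors. The outcome is not a prognostic variable, so on this wording it is not in the imputation model, although no sentence excludes it outright. The section then states: "Regression analyses will be evaluated for FAS and conducted on imputed data". It goes on: "Backward elimination with a significance level of 0.05 will be applied to stepwise automatically select relevant predictors", and "Effect estimates and p-values will be given for each (potential) predictor".

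The SAP describes no multiple imputation, variance correction or complete-case analysis. It adds: "Modification of this imputation strategy is possible if implied by the data", and names no alternative. SAP 6.7 deals only with missing items within rating scales, and Protocol 9.7 is silent on missing predictors.

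**The concern.** Two features of the plan are open to question. One completed data set is treated as real, so the model's standard errors may not reflect that some values were estimated. And the imputation model omits the outcome, which is known to weaken associations when imputed values are drawn at random.

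Some missing data are to be expected. The data are mainly retrospective, patients need at least 12 months on LCIG with no upper limit, and Table 7-2 lists "UPDRS V prior to LCIG initiation (if available" as a predictor. The symptom checklists behind the count predictors also allow an unknown answer (SAP 6.3).

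At stake is the secondary objective of identifying predictors of monotherapy. The p-values decide which predictors survive elimination, so an error in the completed data affects both the reported estimates and the list of predictors.

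**Working it through.** **The plan's own figure.** The documents give no figure for the regression or the imputation. The stated sample size does reproduce: 1.96² × 0.5 × 0.5 / 0.05² = 384.16, rounded up to 385 (Protocol 9.5). That number is used as N below.

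**Inputs from the documents.** N = 385. The outcome rate is about 38%, within the 36-40% monotherapy reported for the registry in Protocol 7.0. The selection level is 0.05.

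**Assumptions not in the documents.** Missing share 10-45%; true odds ratio 1.5 per SD; normally distributed predictors. Setting A has one incomplete and one complete predictor (R-squared between them 0.05-0.5; 1,000 replicates). Setting B has ten predictors, five of them incomplete (pairwise correlation 0.3 and 400 replicates in the 25% and 40% runs).

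**1. Random draw, outcome omitted.** Let m be the share missing at random and β the coefficient given the other predictors. A drawn residual has the right spread but is unrelated to the outcome. Only the observed share (1 − m) carries the association, so the fitted coefficient is roughly (1 − m)β. The simulations agree (share of the true log odds ratio recovered, with 95% coverage where available):

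| Missing | 1 − m | Setting A | Setting B |
|---|---|---|---|
| 10% | 0.90 | 0.91 (95%) | – |
| 15% | 0.85 | – | 0.84 |
| 20% | 0.80 | 0.82 (91%) | – |
| 25% | 0.75 | – | 0.79 (90%) |
| 30% | 0.70 | 0.70 (84%) | 0.71 |
| 40% | 0.60 | 0.59 (71%) | 0.64 (78%) |
| 45% | 0.55 | – | 0.58 |

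In setting A at 30% missing (R-squared 0.2), the odds ratio is 1.33 instead of 1.50: ln 1.33 / ln 1.50 = 0.285 / 0.405 = 0.70. Power is 64% against 78% with multiple imputation. The complete, correlated predictor is inflated to 1.21 times its true log odds ratio. The standard error is 0.124 against 0.154 with multiple imputation, about 19% smaller. The coverage loss is nevertheless mainly bias: in setting B the model standard error is 0.96-0.98 of the empirical spread.

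**2. Predicted value only, outcome omitted.** A filled-in value lies exactly on the regression on the other predictors, so it adds almost nothing to the estimate of β, which then rests on the patients with the value observed. That predicts no attenuation.
- Setting A: 1.01-1.03 of the true log odds ratio, with model standard error over empirical spread 0.95-1.04.
- Setting B, 25% missing: 1.06 (complete data 1.04), ratio 1.03, coverage 96.5%.
- Setting B, 40% missing: 1.07, ratio 0.85 (0.86 for a null predictor), coverage 93.5%, type I error 6.0%. The same run gives ratios of 0.95 with complete data and 0.91 with multiple imputation. The Monte Carlo error of such a ratio is about 1/√(2 × 400) = 3.5%, so part of the shortfall is noise.
- Setting B, 45% missing: standard errors about 17% too small, and power 22% against 54% with multiple imputation. As there is no attenuation, this power loss reflects unstable estimates: the filled-in values are linear functions of one another.

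**3. The candidate remedies.** Multiple imputation with the outcome included, pooled by Rubin's rules, gives odds ratio 1.52, standard error 0.154 and coverage 94% (setting A, 30% missing). Adding the outcome to a deterministic single imputation gives odds ratio 1.84 instead of 1.50, and 20% type I error for a null predictor (setting B, 25% missing). Changing only the list of imputation variables would make matters worse.

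Backward elimination itself was not simulated. Its behaviour is inferred from the single-coefficient p-values and power.

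**The case against.** The best defence is that the plan's words describe the mild version. Missing values are said to be predicted, and no residual is mentioned. On that reading there is no attenuation, coverage is close to nominal up to about 30% missing, and leaving out the outcome is right for a deterministic fill, as step 3 shows. This stands, and it limits the point considerably. It does not close it: SAP 2.5 makes the described methods mandatory for programming, yet two programmers could both follow 7.8 and obtain, at 30% missing, either a nearly unbiased log odds ratio or one about 30% too small.

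The extent of missing data is also unknown. Only UPDRS V is marked as dependent on availability, and the second model uses physician and site variables, to which the argument from old patient charts does not apply. At 10% missing even a random draw keeps 95% coverage in setting A. This stands, and is why the harm is given as a range.

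A reader might infer that reported confidence intervals will be too narrow. For these models the SAP promises estimates and p-values; the intervals in SAP 7.1 are for proportions. The argument therefore concerns p-values and selection.

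Finally, the study is called exploratory and the imputation may be modified. That permits a repair after the data are seen but specifies none.

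**Conclusion.** The concern holds in a limited form. SAP 7.8 imputes once, omits the outcome and makes no allowance for imputation, while leaving open the choice that decides how much this matters.

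- With a random draw, log odds ratios fall to about 0.84, 0.71 and 0.58 of the truth at 15%, 30% and 45% missing.
- With predicted values, there is little harm up to about 30%. At about 40-45% missing in several predictors, standard errors are about 15% too small and power is lower than with multiple imputation.

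These sizes rest on the assumed missing rates, effect size and correlations listed above.

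A reader might conclude that the plan as written will attenuate odds ratios and preferentially discard true predictors that have missing data. The documents do not support that: attenuation needs a random draw, which the SAP does not state, and no elimination run was made to show preferential dropping. Nor does the point touch the primary monotherapy percentages, which do not use imputed predictors. It bears on the estimates, p-values and selection for one secondary, exploratory objective. A better standard method is available at low cost, so the change should be made.

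**What to change.** Replace the imputation paragraph of SAP 7.8 with the following, adopted together:

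- Fully conditional multiple imputation (for example PROC MI and PROC MIANALYZE), at least 20 data sets, with the 12-month monotherapy outcome and all candidate predictors in the imputation model.
- Backward elimination at 0.05 on Wald tests pooled by Rubin's rules, with pooled estimates and p-values reported.
- A complete-case sensitivity analysis, shown beside the missing counts per predictor that SAP 7.1 already provides for.

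The outcome must not simply be added to the existing single imputation.

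Three details belong in the same paragraph. The total symptom count is the sum of three other listed predictors, so it should be derived after its parts are imputed. GNI is determined by country, so the two cannot both enter an imputation model as free terms. Time to onset of morning akinesia is defined only for patients who have it (SAP 6.3), so its blanks in other patients need their own rule.

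Cost: one SAP paragraph, more programming and a more laborious selection step. No new data are needed.

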Obbvie Duodopa® (Levodopa-Carbidopa Intestinal Gel –LCIG-) P16-831 Protocol

Title Page

Title	COSMOS - COmedication Study assessing Mono- and cOmbination therapy with levodopa-carbidopa inteStinal gel (P16-831)			
Protocol Version Identifier	Original Protocol			
Date of Last Version of Protocol	14 th June 2017			
EU PAS Register Number	Study not registered			
Active Substance	Not applicable			
Medicinal Product	Not applicable			
Product Reference	Not applicable			
Procedure Number	Not applicable			
Marketing Authorisation Holder(s)	EU AbbVie Ltd. [name]			
Joint PASS	Not applicable			
Research Question and Objectives	The primary objective of this multi-country, retrospective and cross-sectional, post-marketing observational study (PMOS) is to evaluate the percentages of Advanced PD patients on LCIG monotherapy right after LCIG initiation and at 3, 6, 9, and 12 months, respectively. The secondary objectives are • To describe PD medication management, and the main reasons justifying their use, directly prior to LCIG initiation, at LCIG initiation and during long-term LCIG treatment • To describe LCIG infusion settings and substantial dose adjustments (section 9.2.7.7) and the respective reasons • To describe the Healthcare Resource Utilization (HCRU) • To identify the physician's and patient's/caregiver's overall preference for the pharmacological treatment approach using LCIG as monotherapy (section 9.2.7.7) vs. LCIG plus add-on PD medication • To identify predictors for achieving long-term monotherapy (section 9.2.7.7) with LCIG vs. LCIG plus add-on PD medication, based on the patient's profile and the physician's profile			

Author	GMA and ad hoc functions				
Country(-ies) of Study	Approximately 15 countries in Europe (Austria, Bulgaria, Croatia, Romania, Czech Republic, Estonia, Hungary, Ireland, Germany, Netherlands, Slovakia and Spain), Canada and Australia, among others; final list of participating countries to be confirmed				
	To investigate all of the above objectives for the participating countries who have enrolled a minimum of 20 study subjects				
	 To describe the latency from the initiation of LCIG therapy until the introduction or tapering of each PD medication, or until substantial dose adjustments of LCIG 				
	 To describe the latency from LCIG initiation until LCIG is given as a monotherapy and the average duration of LCIG monotherapy. 				

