Two-sided 95% confidence intervals will be provided for primary and secondary endpoints defined by proportions. Confidence intervals will also be calculated for differences between pre-defined groups of patients, if appropriate (e.g. LCIG monotherapy vs. LCIG plus add-on PD medication).

Logistic regression and subgroup analyses will be applied to investigate the impact of potential prognostic factors on the primary endpoints and to identify predictors for LCIG monotherapy.

Milestones: Enrollment will be completed within approximately 12 months.

Planned start date (FPI) 15th Dec 2017

Planned end date (LPO) 15th Dec 2018

Final Report of Study Results (CSR) 15th November 2019

Amendments and Updates 5.0

Not applicable

6.0 **Milestones**

Major study milestones and their planned dates are as follows:

15th December 2017 Start of Data Collection (FPI): 15th December 2018 End of Data Collection (LPO): Not applicable Study Progress Report X: Interim Report X: Not applicable Registration in the EU PAS register Not applicable 15th November 2019 Final Report of Study Results:

7.0 **Rationale and Background**

Parkinson's disease (PD)

Parkinson's disease (PD) is a chronic and progressive neurodegenerative disorder with a worldwide estimated prevalence of 0.3% in the general population 40 years of age and older [1]. As incidence and prevalence rise with age, more than 1% of the population over the age of 65 is afflicted with PD [12-14]. The mortality for elderly PD patients is two to five times higher than in age-matched controls [15]. PD is caused by idiopathic degeneration of dopamine-producing cells in the *substantia nigra* of the midbrain [16]. The resulting dopamine depletion disrupts connections to the motor cortex and the thalamus, leading to the clinical cardinal signs of PD: resting tremor, cogwheel rigidity and bradykinesia, along with postural instability [17]. Additional diagnostic criteria are asymmetrical onset of symptoms and symptomatic response to levodopa (LD) [17, 18]. Due to PD's distinctive clinical signs and for the lack of confirming diagnostic tests, diagnosis is generally based on the clinical picture and supported by the observation of a clinical improvement upon dopaminergic drug therapy [19-21].

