The primary objective of this multi-country, retrospective and cross-sectional, postmarketing observational study (PMOS) is to evaluate the percentages of Advanced PD patients on LCIG monotherapy right after LCIG initiation and at 3, 6, 9, and 12 months, respectively.

The secondary objectives are:

- To describe PD medication management, and the main reasons justifying their use, directly prior to LCIG initiation, at LCIG initiation and during long-term LCIG treatment
- To describe LCIG infusion settings and substantial dose adjustments and the respective reasons
- To describe the Healthcare Resource Utilization (HCRU)
- To identify the physician's and patient's/caregiver's overall preference for the pharmacological treatment approach using LCIG as monotherapy vs. LCIG plus add-on PD medication
- To identify predictors for achieving long-term monotherapy with LCIG vs. LCIG plus add-on PD medication, based on the patient's profile and the physician's profile
- To describe the latency from LCIG initiation until LCIG is given as a monotherapy and the average duration of LCIG monotherapy
- To describe the latency from the initiation of LCIG therapy until the introduction or tapering of each PD medication, or until substantial dose adjustments of LCIG
- To evaluate the percentage of patients who are on LCIG monotherapy, PD medication management and HCRU for the participating countries who have enrolled a minimum of 20 study subjects.

9.0 **Research Methods**

9.1 **Study Design**

This is a multi-country, retrospective and cross-sectional, post-marketing observational study (PMOS) of patients with APD treated with LCIG in a routine clinical setting. Patients who are receiving LCIG according to the approved local product label and reimbursement guidelines will be asked to participate.

This study will include a retrospective section, collecting below specified data from patient's medical records from the time of the decision to start LCIG treatment until the present day, and a single study visit (cross-sectional) with clinical status and subjective assessments of patients at present time.

Patients, who have received LCIG for at least 12 months, and who satisfy all the inclusion criteria and none of the exclusion criteria will be eligible to be enrolled into this PMOS. All eligible LCIG patients will be identified consecutively and offered the opportunity to participate in the study.

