To assess the generalizability of the data from the patients enrolled, the physician will be asked to document on a separate Case Reporting Form the number of patients who are eligible but refuse to participate in the study. Only age ranges (<30 years, 30-45 years, 45-65 and > 65 years) and reason(s) for not participating will be collected.

The primary endpoint of this PMOS will be the percentages of APD patients on LCIG monotherapy right after LCIG initiation and at 3, 6, 9, and 12, respectively.

The secondary endpoints are:

- Descriptive data from patient's PD medication:
 - For add-on PD medication: percentage of patient on each PD medication (by drugs and class), total daily dose and levodopa equivalent Daily dose (LEDD), posology (number of times per day);
 - For LCIG infusion settings and substantial dose adjustments: total dose per day and specific for each type of dose (morning dose and continuous dose) and number of hours of infusion.

- Tapering process: number of days required for the tapering process, total dose per day and posology for add-on PD medication prior to LCIG initiation, at LCIG initiation (titration) or during ongoing LCIG treatment
- Main reasons for introduction or tapering of add-on PD medication or LCIG substantial dose adjustments
- Latency and duration of treatments data:
 - Number of days or months from LCIG initiation until LCIG is given as a monotherapy and the duration of LCIG monotherapy.
 - Number of days or months from LCIG initiation until the introduction or tapering of each PD medication, or until any LCIG substantial dose adjustments.
- LCIG monotherapy vs LCIG plus add-on PD medication data:
 - Healthcare Resource Utilization, as measured by Healthcare Resource Utilization Questionnaire (HCRU)
 - Patient's, caregiver's, and physician's overall preference on LCIG monotherapy vs. LCIG plus add-on PD medication, percentage of patient's and physician's preference for each of the options
 - Predictors for LCIG as monotherapy vs. LCIG plus add-on PD medication based on the patient's profile, including socio-demographics, clinical status (motor and non-motor symptoms), Levodopa-equivalent dose (LED), PD medication and Quality of Life
 - Predictors for LCIG as monotherapy vs. LCIG plus add-on PD medications based on the physician's profile including experience as measured by number of years on APD patient management, number of years using LCIG therapy, and number of patients on LCIG therapy

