LCIG monotherapy is defined as being treated with LCIG as the only PD medication that the patient is taking during the LCIG infusion hours. LCIG long term monotherapy is defined as a time period of at least 12 months of continuous LCIG monotherapy.

9.2.7.8 **Current APD Status at study visit**

Parkinson's disease status will be measured by the physician using the following scales: mentation/behaviour/mood (UPDRS I), activities of daily living (UPDRS II), motor examination (UPDRS III), complications of therapy (UPDRS IV) and Modified Hoehn and Yahr Stage (UPDRS V), non-motor symptoms (NMSS) will be recorded and Mini-Mental State Examination (MMSE).

The patient will be requested to fill in the following questionnaires:

- Questionnaire for Impulsive-Compulsive Disorder in Parkinson's Disease- Rating Scale (QUIP-RS)
- Parkinson's disease Sleep Scale Version 2 (PDSS-2).

9.2.7.9 **Healthcare Resource Utilization**

The HCRU Questionnaire will contain questions on the occupational status, nursing home visits, hospitalizations, emergency care visits, caregiver support, including the patient's opinion on PD medication as retrieved by the following questionnaires, which the patient will be requested to complete:

Beliefs Medication Questionnaire (BMQ)

In addition, the patient/caregiver will be requested to state their overall preference on LCIG as a monotherapy vs. LCIG plus add-on PD medication.

Quality of Life 9.2.7.10

In order to assess the patient's quality of life, the patient will be asked to complete the Parkinson's disease Quality of Life Questionnaire (PDQ-8).

Table 1 Summary of assessments

Observation	Before LCIG initiation	LCIG initiation	During LCIG treatment	Patient visit
2	Retrospect	ive Data from Patie		
Center Characterization	X			
Physician experience and treatment preference	X			
Patient demographics	X			
Patient socio- demographics	X			X
Medical History and PD History	X			X
PD medication before starting LCIG	X			
Reason(s) for LCIG initiation		Х		
LCIG infusion data		X	х	X
Add-on PD medication since LCIG initiation		X	X	X
Concomitant Medication (non-PD treatment)	х	X		X
Behaviour/mentation/mood (UPDRS Part I)				X
Activities of daily living (UPDRS Part II)				X
Motor examination (UPDRS Part III)				X
Treatment complications (UPDRS Part IV)				X
Disease Stage (ModifiedHoehn & Yahr stage, UPDRS Part V)	x			х
Non-motor Symptoms Scale (NMSS)				X
Questionnaire for Impulsive-Compulsive Rating Scale (QUIP-RS)				X

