Two-sided 95% confidence intervals will be provided for primary and secondary endpoints defined by proportions. Confidence intervals will also be calculated for differences between pre-defined groups of patients, if appropriate (e.g. LCIG as monotherapy vs. LCIG plus add-on therapy).

Logistic regression and subgroup analyses will be applied to investigate the impact of potential prognostic factors for LCIG monotherapy. Potential prognostic factors used for the regression model will include demographic variables (ie. age, gender, race) and baseline disease characteristics at LCIG initiation (PD duration, hours of OFF time, hours of dyskinesia, Levodopa equivalent daily dosage).

Details of statistical methods will we presented in a separate statistical analysis plan (SAP). All statistical analyses will be carried out by means of the SAS® package (version 9.4 or higher).

9.8 **Quality Control**

The personnel at each PMOS site may be trained on the protocol and PMOS procedures by a CRA at a site training visit, via telephone or on-site.

Throughout the PMOS, the CRO and AbbVie will periodically follow-up with sites to ensure that SAEs and PCs are being reported.

All PMOS data will be entered into the eCRF which will be accessed via a web-based EDC system. Any necessary corrections will be made to the database and documented via queries, source data clarification form or audit trail. A manual review of elected line listings will also be performed at the end of the PMOS. A clinical monitor working on behalf of AbbVie will perform a final site closure visit when the site or study is closed.

9.9 **Limitations of the Research Methods**

The primary limitation of this PMOS is that it is performed in an open-label, noncontrolled and non-randomized design with mainly retrospective data capturing. Thus, selection and reporting bias cannot be excluded. In order to minimize these biases, all eligible patients shall be enrolled in a consecutive manner.

Moreover, as only patients on current LCIG therapy are included, data of patients who discontinued treatment will not be collected. Therefore, comprehensive safety conclusions may not be drawn from the study results.

Finally as the study aims to identify treatment predictors based on patient's and physician's profiles; however it can be influenced by LCIG country specific prescription or reimbursement status. Therefore, country origin would be taken into account when analyzing treatment predictors.

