#### 6.4 Primary variable

There are two primary variables:

1. LCIG monotherapy 1 (yes, no) at LCIG initiation and at 3, 6, 9, and 12 months after LCIG initiation

with the following definition:

- LCIG monotherapy means that the patient is not on any add-on PD medication or PD therapy at the respective time point.
- 2. LCIG monotherapy 2 (yes, no) at LCIG initiation and at 3, 6, 9, and 12 months after LCIG initiation

with the following definition:

LCIG monotherapy means that the patient is allowed to take an add-on PD medication or PD therapy at the respective time point, however, only in the evening after the LCIG infusion is completed (i.e. reason for start of add-on PD medication: other).

Additional specifications for both variables are:

- Medications for indications secondary to PD are allowed.
- If the reason for add-on PD medication is missing the medication will be considered as taken during LCIG infusion (i.e. no monotherapy).
- LCIG initiation date is the start date of the first LCIG infusion.
- 3 months after LCIG initiation is calculated as LCIG initiation date + rounded (3 [months] x 30.4 [days]). 6, 9, and 12 months after LCIG initiation will be calculated analogously.
- For LCIG initiation date with missing day the 15th will be used.

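### SAP 7.8 models monotherapy status on day 365, but the stated objective is predictors of long-term monotherapy (at least 12 continuous months), and no planned model uses that outcome

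*SAP*

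**What the plan says.** **Objective.** The protocol title page reads "To identify predictors for achieving long-term monotherapy (section 9.2.7.7) with LCIG vs. LCIG plus add-on PD medication" and so points to the section that defines the term. Protocol 4.0, protocol 8.0 and SAP 3.2 repeat the objective without the cross-reference: "To identify predictors for achieving long-term monotherapy with LCIG vs. LCIG plus add-on PD medication".

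**Definition.** Protocol 9.2.7.7: "LCIG long term monotherapy is defined as a time period of at least 12 months of continuous LCIG monotherapy". It fixes a duration but no calendar start. The SAP does not carry this definition over.

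**Planned models.** SAP 7.8 takes each of the two primary variables in turn. Monotherapy 1 (or 2) "at 12 months after LCIG initiation will be used as dependent (i.e. response) variable" in two logistic models, one with the patient predictors of Table 7-2 and one with the physician and centre predictors of Table 7-3. SAP 6.4 defines both variables as status at a time point, with no duration condition. It counts from the first infusion: "LCIG initiation date is the start date of the first LCIG infusion".

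**Protocol analysis wording.** The term is looser here. The abstract applies logistic regression to look at effects "on the primary endpoints and to identify predictors for LCIG monotherapy". The endpoint list in 9.1 has "Predictors for LCIG as monotherapy vs. LCIG plus add-on PD medications based on the" physician's profile. Section 9.7 says "Logistic regression and subgroup analyses will be applied to investigate the impact of potential prognostic factors for LCIG monotherapy". None of these says long-term.

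**The concern.** Twelve months appears in both places, as a duration in the definition and as a date in the model, so the two are easily taken for the same thing. A report that follows the SAP would present the 7.8 results under the predictor objective of SAP 3.2. Readers would take them as predictors of sustained monotherapy, when they are predictors of what the patient was taking on one day. The predictors need not be the same. A factor linked to restarting add-on medication in the second year, for example, could matter for sustained monotherapy and be invisible on day 365.

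**Working it through.** **1. The date modelled.** SAP 6.4 multiplies months by 30.4 and rounds: 12 × 30.4 = 364.8, so day 365.

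**2. Number of fits.** 2 monotherapy definitions × 2 predictor tables = 4 fits, all on day-365 status.

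**3. Does anything else in the SAP supply the outcome?**
- SAP 6.5 has a duration of monotherapy. It is descriptive and limited to patients with add-on treatment at initiation, so it omits those on monotherapy from the first day.
- SAP 7.5 mentions later time points up to the visit. They are not regression outcomes.
- SAP 7.10 allows extensions if the data suggest them. That permits a model but does not plan one.

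**4. The two outcomes side by side, for hypothetical patients:**

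| Patient | SAP 7.8 (day 365) | Protocol 9.2.7.7 |
|---|---|---|
| A: last add-on stopped day 360, restarted day 370, kept to the visit | yes | no: run of 370 − 360 = 10 days |
| B: add-on until month 13, then monotherapy to month 30 | no | yes: 30 − 13 = 17 months |
| C: add-on tapered by day 20, then monotherapy to a visit in year 3 | yes | yes |
| D: as C, but visit on day 365 | yes | not yet known: 365 − 20 = 345 days |

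A and B show disagreement in each direction. C shows that a late start alone does no harm. D shows that follow-up matters: eligibility guarantees only 12 months on LCIG, so a patient seen at exactly 12 months can qualify only if on monotherapy from the first day.

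**5. What misclassification could do (assumptions, not document figures).** Take a binary predictor split 200/200, a long-term rate of 30% in the reference group, a true odds ratio of 2.0, and misclassification unrelated to the predictor. The other group's rate is then (0.30/0.70 × 2)/(1 + 0.30/0.70 × 2) = 46.2%. The modelled probability in each group is q = Se × p + (1 − Sp) × (1 − p).

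| Se = Sp | q, reference | q, other | Modelled OR | Approximate power |
|---|---|---|---|---|
| 1.00 | 0.300 | 0.462 | 2.00 | 92% |
| 0.95 | 0.320 | 0.465 | 1.85 | 85% |
| 0.90 | 0.340 | 0.469 | 1.72 | 75% |
| 0.80 | 0.380 | 0.477 | 1.49 | 50% |

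This shows a mechanism. It is not an estimate for this study.

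**6. Room for predictors.** Protocol 9.5 needs 385 evaluable patients: 1.96² × 0.25 / 0.05² = 384.15, rounded up, which reproduces. With country as a 14-level factor (the countries listed in SAP 7.8), Table 7-2 has 18 + 2 + 13 = 33 parameters. Total symptoms is the sum of three other entries and GNI is fixed by country, so 31 are free. Table 7-3 has 10 + 13 = 23, of which 22 are free. If 10% to 40% of 385 patients completed a long-term period (assumption), there would be about 38 to 154 events. That is 38/31 = 1.2 to 154/31 = 5.0 per free parameter with Table 7-2, and 38/22 = 1.7 to 154/22 = 7.0 with Table 7-3. The full tables are therefore too large for the added analysis.

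**The case against.** The SAP implements the protocol's operational text, which speaks of monotherapy and of the primary endpoints. Month 12 is the latest planned time point that the minimum follow-up supports for every patient, so it is a reasonable proxy. The study is declared exploratory. All of this stands, and it is why the existing models should stay. It does not make the outcomes the same, and it does not remove the disagreement within the SAP between sections 3.2 and 7.8.

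A second objection is that the obvious repair would be worse. Suppose the outcome required monotherapy on every day from the first infusion to day 365. Protocol 7.0 says other therapies are usually tapered during titration, so patient C, long-term by the definition, would be coded a failure. This is correct, and that outcome should not be the main one.

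A third is that labelling alone would prevent the misreading. It would, but the objective would then have no planned analysis.

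**Conclusion.** The concern holds as a mismatch between a defined objective and the modelled outcome. Every fit in SAP 7.8 answers a question about status on one date, and none answers the question about at least 12 continuous months. Importance is minor to moderate. The number of patients classified differently is unknown because the documents give no rates of stopping or restarting add-on treatment.

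Three stronger readings are not supported:

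- A reader might infer that the SAP breaks its own statement in 2.5 that it is consistent with the protocol. The looser wording is already in the protocol's abstract, 9.1 and 9.7, and the SAP follows it.
- A reader might infer that anyone who stops the last add-on shortly before day 365 is wrongly counted. That is so only if an add-on restarts, or the visit comes, before 12 months have passed.
- A reader might try to size the error as the month-12 percentage minus the lowest of the five planned percentages. The definition has no day-365 deadline. If every patient tapered by day 20 and stayed on monotherapy for years, that difference would be 100 − 0 = 100 points, yet SAP 7.8 would misclassify nobody.

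**What to change.** 1. In SAP 7.8, label the four existing fits *predictors of monotherapy status at month 12*, and state that they do not model long-term monotherapy as defined in protocol 9.2.7.7.

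2. Add one supportive analysis, for monotherapy 1 and for monotherapy 2: time from LCIG initiation to completion of the first 365 consecutive days of monotherapy, whenever that run begins, censored at the study visit. Protocol 9.2.7.5 already collects the add-on start and stop dates. No event can occur before day 365, and patients on monotherapy from the start complete together, so the method for ties should be named.

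3. State in advance a reduced predictor set suited to the number of events.

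4. State how incomplete add-on dates are handled. SAP 6.4 covers only a missing day in the LCIG initiation date, and the non-imputation rule in SAP 6.5 concerns only tapering. State also whether a temporary LCIG interruption ends a run for analysis purposes, since eligibility requires LCIG on only 80% of days in the preceding year.

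The first item costs a sentence or two. The rest needs a derived variable for each definition and up to 2 × 2 = 4 extra fits, from data the protocol already collects. Patients with short follow-up are censored early, events may be few, and the enrolment of current LCIG users only (protocol 9.9) affects the new analysis as much as the old.
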